The study will be conducted in a population of ambulatory, postmenopausal women aged 50-65 (BMI >18.5 and $\leq 30 \text{ kg/m}^2$), with a lumbar spine (L1-L4), femoral neck, and total hip BMD T-score > -2.5, as measured by DXA (see section 3 above). Women with osteoporosis (T score ≤ -2.5) will not be included in the study because at this stage of knowledge we find it unethical not to offer effective treatment to these individuals. We will recruit subjects of all ethnic groups. Covariates known to influence bone mass, including body mass index (BMI), history of smoking > 6 months prior to entry, alcohol use, baseline BMD of the lumbar spine, femoral neck and total hip area, bone fracture history and co-morbidities will be collected and controlled for in the final analysis. The primary endpoint is the change in bone mineral density (BMD) at the L1-4 lumbar spine over one year of study. Changes in BMD at the femoral neck and total hip area will be secondary endpoints. All BMD data will also be used as a tool for future studies power calculation and design. Additional endpoints will include changes in bone turnover markers and inflammatory/osteoclastogenic cytokines. These indices will provide much needed mechanistic information. To determine additional potential mechanisms of action of probiotics on health, we will conduct serial metabolomics analyses in the plasma, as well as serial assessment of plasma thiol/disulfide redox balance. The data will allow us to establish whether VSL#3 prevents bone loss and/or increases bone mass by regulating bone resorption, formation, or both. Based on our own data in mice following ovx, we hypothesize that treatment with VSL#3 will quickly decrease bone resorption and then stimulate bone formation, resulting in improved net BMD at least one site over the 12-month period of study.

4.2. Screening for eligibility: For study subjects identified among patients seen at the Emory-affiliated Endocrinology, Ob/Gyn, Rheumatology and General Medicine clinics, patients will be pre-screened for eligibility using the Emory Healthcare electronic medical record, and potentially eligible subjects will be approached during their clinic visit by a study coordinator or they will be contacted by phone or letter (as described above) to conduct a full screen. For potential study subjects identified outside of Emory-affiliated Clinics, potential subjects will contact the study team by phone and undergo a pre-screening discussion.

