4.6. Randomization and Stratification: Personnel in the Department of Biostatistics and Bioinformatics at Emory University have developed a centralized electronic randomization system that has been successfully used in several clinical studies¹⁶⁻¹⁹. Subjects will be blindly assigned in equal proportions, stratified by age (above and below 58 years) using a pseudo-random-number generator with randomly permuted blocks. These assignments will be stored in a backend database table within the iDataFAX database management system. This method serves to balance the treatment group assignments over the course of the study to ensure that the desired number of subjects will be allocated to each of the treatment groups at any time point during the randomization period. Permuted block sizes will not be disclosed to the blinded study personnel to minimize the likelihood of their being able to predict the next randomization assignment in the series. Briefly, after obtaining informed consent, all eligibility confirmation data will be entered into the web-based data management system by a research coordinator. If the patient meets all eligibility criteria, computer randomization will be performed and the coordinator will be provided with an audit trail of the process including a verifiable link between the unique study ID and treatment assignment. The application will be password protected with access restricted to designated personnel, including the EUH Investigational Drug Pharmacy staff pharmacist who **will dispense blinded study drug for subjects randomized to Arms A or B.**

4.7. Screening, Entry and Follow-up Evaluations: These will occur as outlined in Table 1. Adverse effects and safety data will be reviewed at least every 6 months by a Data Safety Officer, a gastroenterologist senior Emory faculty member with expertise in clinical trials who is unaffiliated with the study, as described below (Section 7.5).

4.8. Procedures to be performed (all for research purposes only):

- **Medical examination:** Medical history and medications will be reviewed by a member of the research team, and a physical exam will be completed by a licensed physician, as required by the clinical research unit. Habitual alcohol intake and dietary calcium intake (based on reported supplements, dairy, and other high-calcium foods) will be assessed.
- **Urine collection:** Urine will be collected for standard urinalysis indexes.

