Compliance with the study placebo or VSL#3 doses will be assessed serially. This will be determined by contacts (twice monthly telephone or at research center visits) of the study coordinator with each subject and responses to three standardized question areas: 1) "Are you having any difficulty, problems or new symptoms with the study medication?" 2) If yes, "What has the problem been?" and 3) "Have you missed any of your study drug doses, and if so how many in the previous 2 week period?" Appropriate notations based on subject responses will be documented in the CRF. Subjects will be instructed at study entry and reminded via serial contacts to return all of their used and unused drug sachets at each CRN visit (6 months +/- 2 weeks and 12 months +/- 2 weeks after entry). Unused and used study drug sachets will be tallied and recorded in the CRF by the study coordinator serially for the entire study. All sachets (used and unused) will be given to the Emory University Investigational Drug Service (IDS) for disposal.

Recruitment and retention will be documented via conventional CONSORT criteria and documentation of missed study visits, missed telephone communications and compliance with study drug administration. All data will be maintained in the CRFs.

4.13. Sample size and power considerations: Longitudinal data from 380 postmenopausal women form the basis for estimating the sample size and power for lumbar spine BMD as the primary outcome endpoint. BMD at the lumbar spine was available at baseline and 6 and 12 months after baseline (883 measurements across the 3 time points). Mean baseline BMD was 1.108 g/cm² (within-subject standard deviation = 0.03 g/cm² and the standard deviation on change = 0.02 g/cm²). Assuming no decline on average in BMD in the VSL#3 treated group and a decline on average of 0.03 g/cm² in the control group and an estimated within-subject standard deviation in each group of 0.03 g/cm², the proposed sample sizes (n=20 postmenopausal women per group) will provide more than 85% power to detect a difference on change of 0.03 g/cm² at the two-sided 5% significance level if the true difference between treatment groups is 0.03 g/cm² (two-sided two-sample equal variance t-test).

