4.14. Statistical analyses: Demographic data will be summarized with standard descriptive statistics. Repeated-measures analyses for each outcome (i.e., GSRS scale scores, BMD) will be performed with a means model via the SAS MIXED Procedure (version 9.4; SAS Institute, Cary, NC), providing separate estimates of the means by time on study (baseline, 1-year and 2-years) and treatment group. The model will include three predictors (treatment arm, time on study and the statistical interaction between treatment arm and time on study). A compound-symmetric variance-covariance form in repeated measurements will be assumed for each outcome and robust estimates of the standard errors of parameters will be used to perform statistical tests and construct 95% confidence intervals²⁴. The model-based means are unbiased with unbalanced and missing data, so long as the missing data are non-informative (missing at random, MAR). A P-value ≤0.05 will be considered statistically significant for the main effects (treatment and time on study) and for the treatment by time on study interaction effect from the repeated measures analysis. The statistical test for interaction between time on study and treatment will be the primary overall hypothesis test to determine whether an outcome in the two study groups changed in significantly different ways during follow-up (i.e., different temporal patterns over time). If a mean outcome in the two groups is consistently different or similar over time (i.e., no statistical interaction) then the main effect test for treatment will be used as the primary test of VSL#3 efficacy. If a significant interaction is detected, then t-tests will be used to compare the differences between the model-based intervention means at each time point and to compare differences over time within each treatment arm. Specific statistical tests will be done within the framework of the mixed effects linear model. Analyses will control for risk factors for osteoporosis, such as age, gender, race, BMI, habitual alcohol consumption, smoking, physical activity, and fracture history, as necessary. All tests will be 2-sided and a P value ≤ 0.05 will be considered significant.

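### Sections 4.1 and 4.14 disagree on covariates and leave their form open; entered as time-fixed main effects, they would not reach the primary arm-by-time test

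*Combined protocol and SAP*

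**What the plan says.** Section 4.1 names BMI, past smoking, alcohol use, baseline BMD at three sites, fracture history and co-morbidities, and makes an unconditional promise: "bone fracture history and co-morbidities will be collected and controlled for in the final analysis".

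Section 4.14 describes a repeated-measures model in which baseline is one level of time on study. It specifies: "The model will include three predictors (treatment arm, time on study and the statistical interaction between treatment arm and time on study". The arm-by-time interaction is the primary test. If there is no interaction, the treatment main effect becomes the primary test of efficacy. The section then says that analyses will control for risk factors, with these as examples: "age, gender, race, BMI, habitual alcohol consumption, smoking, physical activity, and fracture history, as necessary". It gives no rule for deciding necessity, no time for the decision, and no statement of whether covariates enter as main effects or crossed with time.

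Section 4.6 says that allocation is "stratified by age (above and below 58 years". Table 1 and Section 8 schedule DXA at screening or entry and again at 12 months, so BMD has two values per woman.

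**The concern.** The two sections cannot both be followed. One promises control for baseline BMD and co-morbidities; the other omits both and makes everything it lists conditional. Gender cannot be adjusted for in a trial of postmenopausal women. Age drives the randomisation, yet its adjustment is optional and the cut at 58 is not named in the analysis.

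The structure of the model adds a second difficulty. Because baseline BMD is an outcome row, a subject-level covariate added as a main effect shifts both of a woman's rows equally and drops out of the contrast that is tested first. A reader of Section 4.1 would expect the primary result to be adjusted; under this reading it would not be. At stake are a defined primary test, agreement between sections, and error rates that respect the stratified allocation.

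**Working it through.** **1. The lists side by side**

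| Variable | Section 4.1 | Section 4.14 |
|---|---|---|
| BMI, alcohol, smoking, fracture history | promised | conditional |
| Baseline BMD, co-morbidities | promised | not listed |
| Age, race, physical activity | not listed | conditional |
| Gender | not listed | conditional, but constant |
| Age stratum, cut at 58 | not listed | not named |

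Both lists are open: each is introduced as a set of examples.

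**2. The plan's power figure.** Section 4.13 uses an unadjusted two-sample t-test with 20 per group. The effect is a difference in change of 0.03 g/cm² between arms (zero mean loss on VSL#3, 0.03 on placebo). For the spread it takes "an estimated within-subject standard deviation in each group of 0.03 g/cm²". The noncentrality is 0.03 / (0.03 × √(2/20)) = 3.16 on 38 degrees of freedom. Power at two-sided 5% is 86.9% (88.5% by normal approximation), so the stated figure of more than 85% reproduces.

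**3. Why a main-effect covariate cancels.** Write the two rows for woman i as

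Y(i,0) = μ + α·arm + γ·Z + b + e₀

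Y(i,1) = μ + α·arm + τ + δ·arm + γ·Z + b + e₁

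The change is τ + δ·arm + (e₁ − e₀). Both γ·Z and α have gone. With complete data the estimate of δ is the difference in mean change between arms, whatever Z is.

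**4. Numerical check.** One simulated 40-woman data set was used at each missingness level. Assumptions: between-subject SD 0.15, SD of change 0.03, four covariates, compound symmetry, robust SEs. Section 4.14 labels follow-up as 1 and 2 years; rows here follow the DXA schedule (baseline and 12 months).

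| Missing at 12 months | No covariates | Main effects | Covariate × time |
|---|---|---|---|
| 0% | 0.027849 | 0.027849 | 0.020196 |
| 10% | 0.031329 | 0.031294 | 0.028429 |
| 20% | 0.024076 | 0.024413 | 0.025668 |

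With complete data the robust SE is 0.010096 with and without main-effect covariates. With missing data the shifts are 0.000035/0.031329 = 0.1% and 0.000337/0.024076 = 1.4%.

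The fallback test does respond. With complete data the arm coefficient (the baseline-row difference) moved from −0.0295 to −0.0166. Adding half the interaction gives the difference averaged over both visits: −0.0295 + 0.0139 = −0.0156 without covariates, and −0.0166 + 0.0139 = −0.0027 with them.

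**5. Upper bound on the open choice.** Seven listed covariates are not constant, giving 2⁷ = 128 sets. Over 1,500 null trials, the smallest P across all sets was at or below 0.05 as follows (simulation error about 1 point):

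- Treatment main-effect test: 11% if covariates explain none of the outcome, 17% if they explain an assumed 30%.
- Interaction with covariate-by-time terms: 10% and 18%.
- Interaction with main effects only and complete data: no inflation, by step 3.

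**6. What the proposed model gains.**

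*Baseline BMD.* The ANCOVA variance ratio is (1+ρ)/2, with ρ = 1 − SD²(change)/(2·SD²(between)). For SD of change 0.03 and assumed between-subject SD 0.10, 0.15 and 0.18, power is 87.6%, 87.2% and 87.1%, against 86.9%. If the 0.03 were instead the SD of a single measurement, the SD of change would be 0.03 × √2 = 0.0424, and power would go from 58.7% to 59.3–60.7%.

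*Age stratum.* Assume equal strata whose mean BMD change differs by g. Stratified allocation removes g from the true variance of the arm difference, but an unadjusted test still counts g²/4 in its pooled variance. For g = 0.02 the SD used becomes √(0.0009 + 0.0001) = 0.0316; for g = 0.03 it becomes √(0.0009 + 0.000225) = 0.0335. The SE is therefore about 5% and 12% too large. In simulation the unadjusted change test ran at 3.8% and 2.6% instead of 5% and lost about 2 and 5 power points. ANCOVA with the stratum held 5% and about 86% power. If age is unrelated to change there is no gain.

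**The case against.** The main-effects form is an inference. Section 4.14 says only that analyses will control for risk factors within the mixed model. Alcohol intake and physical activity are recorded again at 6 and 12 months, so time-varying use is possible, and covariate-by-time terms are not excluded. This stands, and it is why the cancellation must be stated with its conditions.

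A reader might infer that the plan gives no adjustment at all. It does not follow: covariates reach the fallback treatment main-effect test, which Section 4.14 can make the primary test of efficacy. Nor is the stratifier ignored: age heads the list in 4.14, though conditionally and without the cut. That baseline BMD is both outcome and covariate emerges only when 4.1 and 4.14 are read together.

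A reader might also infer that the primary interaction P value is inflated to 10–18%, or that a long covariate list erodes its power. Neither can be true of the test from which main-effect covariates cancel. The inflation needs terms that the plan does not state and a search over every subset. Section 7.5.6 keeps the statistician and investigators blinded until the endpoints are analysed, which limits selection guided by treatment identity. It does not fix the covariate set, and results coded by arm would still show P values. Nothing in the documents shows that the choice would be made after results are seen; they are silent on timing.

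**Conclusion.** The concern holds as an inconsistency between sections and a gap in prespecification. Sections 4.1 and 4.14 must be reconciled. Under the natural but unstated reading, neither the promised adjustment nor the age stratum reaches the primary arm-by-time test: exactly so with complete data and time-fixed main effects, and nearly so in the simulated data with 10–20% missing. The open choice then bears on the fallback test alone, with a worst case of 11–17%. It bears on the interaction (10–18%) only if covariate-by-time or time-varying terms are added. These are upper bounds.

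Between-subject SD, variance explained, missingness and the stratum gap are assumptions; the documents do not give them. The benefit of correction is a defined primary test, consistent sections, and correct error rates if age predicts BMD change. It is not power: baseline BMD adds 0.2 to 0.7 points at SD of change 0.03.

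**What to change.** In Section 4.14 state one primary model for lumbar spine BMD: ANCOVA of the 12-month value (or the change) on arm, baseline lumbar spine BMD and the randomisation age stratum, with no other covariates. If the mixed model is kept, enter the age stratum crossed with time. Put the remaining risk factors in one named sensitivity analysis with a closed list, and state the form in which each enters. Delete gender and the qualifier *as necessary*. Use the same list in Section 4.1, and record that it is fixed before unblinding.

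The cost is wording. The variables are already in the collection plan and the sample size does not change. The sponsor gives up the freedom to choose covariates later.

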5. DRUG DOSING

5.1. Method for determining doses: Doses were based on the concentration of colony forming units (CFU) within a single, commercially available sachet, and doses used in previous trials in adults with inflammatory bowel diseases (IBD), irritable bowel syndrome, and other gastrointestinal (GI) disorders²⁵⁻³¹.

5.2. Maximum Dosage: The maximum dosage will be 900x10⁹ CFU orally daily. This or higher doses have been used in most trials designed to assess the tolerability and efficacy of VSL#3 in IBD and irritable bowel syndrome in adults.

5.3. Drug duration: Patients will take the drug for 1 year.

5.4. Distribution and Storage of Investigational Products: The study drug/placebo will be delivered to the EUH Investigational Drug Service (IDS) directly from the manufacturer. The EUH IDS will store the study drug/placebo under the appropriate storage conditions, as indicated by the manufacturer. The Pharmacy will dispense the study drug/placebo to study subjects (who will remain blinded). Subjects will be provided with sufficient study drug product every two months. IDS will dispense a 2-month supply of the study drug sachets to the study team for each subject serially, who will over-night mail the resupply with a commercial carrier in sealed Styrofoam containers containing cold packs. The IDS will provide subjects with instructions for study drug storage at home. For all products provided, the lot number and expiration date will be recorded in individual subjects case report forms. All study drug products will be labeled with the following, "Caution: New Drug—Limited by Federal (United States) law to investigational use."

6. OBSERVATIONS AND MEASUREMENTS FOR STUDY OBJECTIVES

Please see Sections 4.8-4.10 and Table 1 above.

7. PROCEDURES TO MONITOR DRUG EFFECTS AND MINIMIZE RISK

7.1 Potential Risks/Discomforts

The risk of participating in this study is minimal.

- a. **VSL#3:** There are few reported side effects of this dietary supplement. Some studies have reported GI effects, such as bloating abdominal pain. Of note, VSL#3 doses of up to 3600×10^9 CFU orally daily for several weeks or months have been reported to be well-tolerated in adults with irritable bowel syndrome, Crohn's disease, and other GI disorders ³²⁻³⁷.
- b. **Venipuncture:** There is some minor discomfort and risk of mild bruising during venipuncture. Standard aseptic techniques will be used during phlebotomy; thus, infection is unlikely. Disposable pre-sterilized needles and syringes will be used for all blood drawing in this study; needles and syringes will not be reused.
- c. **DXA:** DXA involves exposure to small amounts of radiation. The radiation dose is equal to or less than the amount of background radiation received in a round-trip flight from New York to Los Angeles or the natural environmental radiation the average person receives in the United States annually. The risk from radiation exposure of this magnitude is considered to be negligible when compared to everyday risks. For screening purposes, if menopausal status is not clear, a urine pregnancy may be performed prior to DXA testing.
- d. **Stool collection:** There may be minor inconvenience from the process of collecting a small stool sample, placing a stool sample into the shipping tube and shaking it for a few seconds to mix.
- e. **BIA:** The BIA machine passes a weak electrical current through electrodes attached to hands and feet. Participants will not feel anything. There are no known risks associated with the procedure, although participants who have pacemakers or other implantable electronic devices will not undergo the BIA procedure.
- f. **Other:** Additional risks will be associated with confidentiality issues surrounding the collection/recording of data, but steps will be taken to minimize these risks, as described below.

7.2. Assessment of Risk/Benefit

- a. **Direct benefit:** Participants will be compensated a stipend for their time and inconvenience. Participants will also receive information on their measured bone density after the 12-month period. Participants will be encouraged to share the results with their healthcare providers. There may be no specific health benefit to patients' participation in the study.
- b. **Indirect benefit:** The long-term goal of this study is to identify a safe, well tolerated and simple intervention strategy, using a commercially available combination probiotic to minimize bone loss associated with menopause. If our hypothesis is correct, VSL#3 would be an inexpensive, easily obtainable commercial probiotic that could be supplemented in this population.
- c. The anticipated benefits of the proposed research study outweigh the potential risks to participating subjects. The risks incurred are minimal relative to the potential benefit of finding an effective therapy to reduce bone loss in postmenopausal women.

7.3. Procedures to monitor drug effects

Patients will be called every other week to maintain compliance/adherence with the study drug regimen and to monitor for any adverse effects. Questions will also focus on gastrointestinal symptoms (via the GSRS score), as these are the primary expected side effects of VSL#3. In addition to twice monthly phone calls, subjects will be asked to complete **Subject Diary Cards** to capture adverse events during the course of the trial and up to 1

month following the cessation of the study drug. Subjects will receive a final safety follow-up phone call 1 month following the cessation of the study drug.

Systemic reactions and adverse events (AEs) (e.g. diarrhea, headache, fatigue, rash, and myalgia) will be monitored every other week during study phone calls. The intensity of these events will be assessed on a standard toxicity grading scale for healthy volunteers³⁸, as shown in **Table 3**. Standard laboratory values will be assessed at baseline, 6 month and 12 month visits and graded as shown in **Table 4**. Decisions to withdraw the study drug from individual subjects, will be at the discretion of both the PI and a Safety Officer (described below), based on a severity grade of 3 or 4 for Graded Adverse Events or Laboratory Values, and based on the likelihood of it being related to study.

Table 3. Graded Adverse Events

Adverse Event	Mild (Grade 1)	Moderate (Grade 2)	Severe (Grade 3)	Potentially Life Threatening (Grade 4)
Nausea/vomiting	No interference with activity or 1 – 2 episodes/24 hours	Some interference with activity or > 2 episodes/24 hours	Prevents daily activity, requires outpatient IV hydration	ER visit or hospitalization for hypotensive shock
Diarrhea	2 – 3 loose stools or < 400 gms/24 hours	4 – 5 stools or 400 – 800 gms/24 hours	6 or more watery stools or > 800gms/24 hours or requires outpatient IV hydration	ER visit or hospitalization
Headache	No interference with activity	Repeated use of non-narcotic pain reliever > 24 hours or some interference with activity	Significant; any use of narcotic pain reliever or prevents daily activity	ER visit or hospitalization
Fatigue	No interference with activity	Some interference with activity	Significant; prevents daily activity	ER visit or hospitalization
Myalgia	No interference with activity	Some interference with activity	Significant; prevents daily activity	ER visit or hospitalization
Rash/Erythema	2.5 – 5 cm	5.1 – 10 cm	> 10 cm	Necrosis or exfoliative dermatitis
Pruitis/Itching	No interference with activity	Some interference with activity	Significant; prevents daily activity	ER visit or hospitalization
Fever	38.0 – 38.4 °C 100.4 – 101.1°F	38.5 – 38.9°C 101.2 – 102.0°F	39.0 – 40°C 102.1 – 104 °F	> 40°C > 104 °F
Tachycardia - beats per minute	101 – 115	116 – 130	> 130	ER visit or hospitalization for arrhythmia
Bradycardia -	50 – 54	45 – 49	< 45	ER visit or

beats per minute***				hospitalization for arrhythmia
Hypertension (systolic) - mm Hg	141 – 150	151 – 155	> 155	ER visit or hospitalization for malignant hypertension
Hypertension (diastolic) - mm Hg	91 – 95	96 – 100	> 100	ER visit or hospitalization for malignant hypertension
Hypotension (systolic) – mm Hg	85 – 89	80 – 84	< 80	ER visit or hospitalization for hypotensive shock
Respiratory Rate – breaths per minute	17 – 20	21 – 25	> 25	Intubation
Other illness or clinical adverse event (as defined according to applicable regulations)	No interference with activity	Some interference with activity not requiring medical intervention	Prevents daily activity and requires medical intervention	ER visit or hospitalization

Table 4. Laboratory Adverse Events

Blood Parameter	Reference Range*	Mild/Moderate	Severe/Critical
Sodium – Hyponatremia mmol/L	136-144	126-135	≤125
Sodium – Hypernatremia mmol/L	136-144	145 – 155	≥156
Potassium – Hyperkalemia mmol/L	3.6-5.1	5.2-6.0	>6.0
Potassium – Hypokalemia mmol/L	3.6-5.1	3.0-3.5	<3.0
Glucose – Hypoglycemia mg/dL	65 – 110	45-64	<45
Glucose – Hyperglycemia mg/dL	65 – 110	111-450	>450, or insulin requirement, or hyperosmolar coma
Blood Urea Nitrogen, BUN mg/dL	8-25	26-150	> 150 or requires dialysis
Creatinine – mg/dL	0.4-1.0	1.1-5.8	>5.8 or requires dialysis
Calcium – hypocalcemia mg/dL	8.9-10.3	6.6-8.8	≤6.5
Calcium – hypercalcemia mg/dL	8.9-10.3	10.4-12.9	≥13.0
Albumin – Hypoalbuminemia g/dL	3.5-4.8	<3.5	-----
Total Protein – Hypoproteinemia g/dL	6.1-7.9	<6.1	-----
Alkaline phosphate unit/L	32-91	<91	-----
ALT unit/L	≤ 33	>33	-----
AST unit/L	15-41	>41	-----
Bilirubin mg/dL	0.3-1.2 mg/dL	1.3-20	>20
Cholesterol mg/dL	≤ 199	>199	-----
Hemoglobin (Female) - g/dL	11.4-14.4	6.6-11.3	≤ 6.5
WBC low x 10 ³ /mCL	4-10	2-3.9	< 2.0
WBC high x 10 ³ /mCL	4-10	11-50	>50
Eosinophils x 10 ³ /mCL	<0.36	>0.37	Hyper eosinophilic
Platelets-high x 10 ³ /mCL	150-400	401-999	>999
Platelets-low x 10 ³ /mCL	150-400	51-149	<50

Urine Parameter	Reference Range	Mild/Moderate	Severe/Critical
Protein	none	trace	Hospitalization or dialysis
Glucose	none	trace	Hospitalization for hyperglycemia
Blood (microscopic) – red blood cells per high-power field (RBC/hpf)	none	trace	gross blood or hospitalization or packed red blood cells (PRBC) transfusion

*Specific to EUH Laboratories

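### As printed, Table 4 flags normal alkaline phosphatase and misses raised values; it also gives ALT, AST and alkaline phosphatase no severe class and does not tie its classes to the grades used in section 7.3

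*Combined protocol and SAP*

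**What the plan says.** Section 7.3 sets up the laboratory safety rule in two steps.

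- Grading: "Standard laboratory values will be assessed at baseline, 6 month and 12 month visits and graded as shown in" Table 4.
- Use of the grades: withdrawing study drug from a participant "will be at the discretion of both the PI and a Safety Officer", "based on a severity grade of 3 or 4 for Graded Adverse Events or Laboratory Values", together with how likely the event is to be related to the study.

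Table 3, for clinical events, has four numbered grades, with Severe as grade 3 and potentially life-threatening as grade 4. The laboratory table, "Table 4. Laboratory Adverse Events", has only two classes, Mild/Moderate and Severe/Critical, and no numbers.

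The rows at issue are:

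| Row | Reference range | Mild/Moderate | Severe/Critical |
|---|---|---|---|
| "Alkaline phosphate unit/L" | 32-91 | <91 | dashes |
| ALT | ≤33 | >33 | dashes |
| AST | 15-41 | >41 | dashes |

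Other rows do carry severe limits. BUN has "> 150 or requires dialysis", creatinine has ">5.8 or requires dialysis", and "Bilirubin mg/dL" is severe above 20.

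**The concern.** Table 4 is the only step that turns a laboratory value into the grade named in section 7.3. Three things in it do not work.

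1. The alkaline phosphatase cut-off points the wrong way. It marks in-range values as laboratory adverse events and gives raised values no class.
2. ALT, AST and alkaline phosphatase have no severe class, and Mild/Moderate is open-ended for ALT and AST. For these tests the table cannot separate a trivial rise from a large one.
3. Nothing says which Table 4 class counts as grade 3 or 4.

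At stake are the consistency of the withdrawal decision and the meaning of the laboratory adverse event counts, in a trial whose primary objective (section 2) includes showing that VSL#3 acts safely. No other section fills the gap. The exclusion criteria in section 3.2 set limits for creatinine and GFR, HbA1c and 25(OH)D, but none for liver tests.

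**Working it through.** The plan states no figure to reproduce here. The check applies Table 4 as printed.

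**Alkaline phosphatase (reference 32-91, Mild/Moderate <91).** The reference range holds 91 − 32 + 1 = 60 whole-number values. Those below 91 run from 32 to 90, which is 59. So 59 of 60 normal values are classed Mild/Moderate. No value above 91 satisfies <91, so 1.5 to 20 times the upper limit (136.5 to 1820) gets no class.

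**ALT and AST.** At 1.5, 3, 5, 10 and 20 times the upper reference limit:

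| Test | 1.5x | 3x | 5x | 10x | 20x | Class |
|---|---|---|---|---|---|---|
| ALT (33) | 49.5 | 99 | 165 | 330 | 660 | Mild/Moderate throughout |
| AST (41) | 61.5 | 123 | 205 | 410 | 820 | Mild/Moderate throughout |

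**How unusual the blanks are.** Table 4 has 23 blood rows. A numeric severe limit appears in 16: sodium (2), potassium (2), glucose (2), BUN, creatinine, calcium (2), bilirubin, hemoglobin, WBC (2) and platelets (2). Eosinophils has a word only (1). Dashes appear in 6: albumin, total protein, alkaline phosphatase, ALT, AST and cholesterol. 16 + 1 + 6 = 23. Bilirubin's severe limit is 20/1.2 = 16.7 times its upper reference limit, and it does not grade an enzyme rise.

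**Link to grade 3 or 4.** There are two possible readings.

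- Severe/Critical means grade 3-4. Table 3's labelling of Severe as grade 3 suggests this, but no text states it. Then ALT, AST and alkaline phosphatase can never produce a grade 3-4 laboratory value.
- It does not mean that. Then no Table 4 row carries a grade 3 or 4, and the laboratory part of the criterion cannot be applied to any test.

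**Number of results touched.** Table 1 schedules post-baseline chemistry at months 6 and 12, so 40 × 2 = 80 results without dropout. If 80% to 100% of alkaline phosphatase values are in range (an assumption; the documents give no figure), a literal reading classes 80 × 0.80 = 64 to 80 × 1.00 = 80 normal results as Mild/Moderate, ignoring any value of exactly 91. For withdrawal, only the month 6 check falls before treatment ends at one year, so at most 40 results per test could inform that decision.

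**Whether the table implies a multiple for a severe limit.** Severe limit over upper reference limit: platelets 999/400 = 2.5; glucose 450/110 = 4.1; WBC 50/10 = 5.0; creatinine 5.8/1.0 = 5.8; BUN 150/25 = 6.0; bilirubin 16.7. The electrolyte rows are lower: sodium 156/144 = 1.08, potassium 6.0/5.1 = 1.18, calcium 13.0/10.3 = 1.26. The spread is too wide to settle a value for the enzymes.

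**The case against.** The strongest reply is that the decision is not mechanical. Withdrawal is discretionary and also weighs relatedness (7.3). Clinicians review the safety laboratory tests (7.4.1), and the Safety Officer reviews safety data at least every six months (4.7). Toxicity and a physician's decision are accepted grounds for stopping treatment (7.5.4). An event that leads to an emergency visit or admission can reach grade 4 through the last row of Table 3. All of this stands. A reader might infer that the drug could not be stopped for a large ALT rise; the documents do not support that. What they lack is a grade for the isolated, asymptomatic rise managed as an outpatient.

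A second reply is that the blanks may be deliberate. The product is described as a supplement with few reported side effects, mainly gastrointestinal (7.1, 7.3), and albumin, total protein and cholesterol are blank too. This is plausible, and it is why the missing limits are an improvement to make rather than an error. The plan does not say that the blanks are intended.

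A third reply is that the <91 entry is a reversed sign that staff would notice, since the correct range is in the next cell, or a fault in reading the PDF. This is likely. The 64 to 80 flagged results are therefore a ceiling under literal use, and a reader should not take them as a forecast of false adverse events. The entry as printed still needs correcting, and the ALT and AST gap does not depend on it.

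The toxicity scale cited as reference 38 does not close the gap, because section 7.3 ties it to Table 3.

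**Conclusion.** The alkaline phosphatase entry is wrong as written, provided that the source table also reads <91: it flags 59 of 60 normal whole-number values and no raised one. The missing link between Table 4 and grades 3-4, and the missing severe limits for three enzymes, are gaps that are cheap to close. The statement that an isolated enzyme rise cannot meet the laboratory criterion rests on reading Severe/Critical as grade 3-4, which is reasonable but not stated.

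The practical reach is small: 40 women and one scheduled chemistry check on treatment before month 12. The documents give no basis for estimating how often a large ALT or AST rise would occur. The primary endpoint, power and efficacy analysis are unaffected.

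**What to change.** 1. Check the source table and change the alkaline phosphatase Mild/Moderate entry to >91.
2. State in section 7.3 that Severe/Critical in Table 4 counts as grade 3 or 4.
3. Add a Severe/Critical limit for ALT, AST and alkaline phosphatase as a multiple of the upper reference limit, chosen by the study clinicians, and cap Mild/Moderate there. Five times is an illustration only: ALT 33 × 5 = 165, AST 41 × 5 = 205, alkaline phosphatase 91 × 5 = 455. Three times gives 99, 123 and 273; ten times gives 330, 410 and 910. Albumin, total protein and cholesterol can stay blank if the protocol says that this is intended.

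The cost is a short amendment to three table rows and one sentence, with no added visits, samples or procedures. The downside is an occasional extra withdrawal review.
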